4.2.3 DSI 18.3 FROM THE HALT-C TRAINING DATASET IS A CLINICALLY MEANINGFUL CUTOFF

As stated at the introduction to this application, the primary objective of this study is to validate DSI \leq 18.3 as a cutoff for "Rule Out" of large esophageal varices. In HALT-C, DSI \leq 18.3 had NPV >99%, NLR 0.0926, and FNR 1%. A person with DSI \leq 18.3 may be able to avoid EGD; reducing healthcare costs, improving clinical management, and enhancing the person's experience.

Patients with large esophageal varices (>5 mm diameter) are at immediate risk for variceal hemorrhage and need urgent treatment. The HALT-C Training dataset indicated that likelihood for large esophageal varices or varices of any size is proportional to DSI, as DSI increases likelihood for both large varices and varices of any size increases. DSI >18.3 had sensitivity 95% and PLR 2.09; "Ruling In" large esophageal varices. A patient with DSI >18.3 may be a candidate for EGD. Performing EGD and initiating treatment due to early detection of large esophageal varices can also reduce health care costs and improve patient management by preventing subsequent variceal hemorrhage and the associated morbidity and mortality.

[figure not shown]

Figure 9: Comparison of DSI with Liver Biopsy

Both fibrosis stage by METAVIR and the range of DSI by HepQuant SHUNT test correlate with risk for any but especially large varices. The DSI cutoff 18.3 has improved diagnostic performance for large varices, compared to histologic diagnosis of cirrhosis.

The cutoff of DSI 18.3 corresponding to sensitivity of 95% (CI 93% to 98%) for large varices compares favorably with the gold standard of biopsy-diagnosed-cirrhosis which has a sensitivity of only 77% (**Figure 9**) and, as noted previously, the current noninvasive practice using LSM plus platelet count. Therefore, fewer cases of dangerous large varices are missed when using DSI.

DSI cutoff of 18.3 also identified the patients with any size varices (52 small and 22 large) with 69% sensitivity (CI 57% to 79%), specificity 58%, PPV of 46%, and NPV of 78%.

Of the 52 patients with small varices, 30 (58%) had baseline DSI >18.3 - 19/30 (63%) experienced clinical outcomes an average of 3.1 ± 1.6 years later, including 10/30 (33%) with liver related death. The remaining 22 (42%) with small varices had DSI \leq 18.3 - 4/22 (18%) experienced clinical outcomes an average of 5.5 ± 1.1 years later, and only 1/22 (4.5%) experienced liver-related death. No patient with small varices at baseline experienced variceal hemorrhage.

The DSI cutoff of 18.3 appears to separate the patients with small varices who are at low risk for clinical outcomes (DSI \leq 18.3) from the patients with small varices who have higher risk for clinical outcomes (DSI >18.3). Given the benign long-term clinical course of subjects with small varices and DSI \leq 18.3 (see also **Appendix B**, Investigator's Brochure), we speculate that these cases may only need serial clinical assessment. That assessment might also include periodic HepQuant SHUNT testing, every 2 to 3 years, and if DSI exceeds 18.3, EGD might be warranted.

4.3 Validating DSI Cutoff 18.3 in the CLD Validation Dataset

4.3.1 DESCRIPTION OF THE CLD VALIDATION DATASET

Characteristics of CLD Patients: The goal is to recruit a population of patients with chronic liver disease (CLD) that spans the spectrum of severity and etiologies of CLD to encompass all CLD patients meeting criteria for EGD to screen for varices. The inclusion and exclusion criteria were selected to encompass severity of CLD ranging from non-cirrhotic fibrosis with low platelet count to moderately compensated Child-Pugh B cirrhosis and to achieve an overall prevalence of large esophageal varices of $\geq 20\%$. Enrolled subjects must satisfy 4 main criteria:

- Meets the protocol-defined definition for chronic liver disease (CLD).
- For patients with CLD with non-cirrhotic F3 disease, platelet count must be <175,000 μL⁻¹. The BAVENO VI criteria used platelet count cutoff of 150,000 μL⁻¹ to enhance the diagnostic performance of LSM. Others have used lower platelet counts of 100,000, 110,000, and 120,000 μL⁻¹. The lower the platelet count the higher the likelihood of large varices or varices of any size. But, as the cutoff for platelet count decreases the number of missed cases of large varices increases.

The goal of the DSI cutoff \leq 18.3 is exclusion of all cases with large esophageal varices. In the HALT-C Training dataset, the prevalence of large varices was 18.3% (17/93) in the cases with F4 fibrosis (cirrhosis), and similar, at 21.8% (17/78), in F4 cases with platelet count <175,000 μ L⁻¹. I n contrast, the prevalence of large varices was 9% (4/44) in all cases with F3 fibrosis, but much higher, at 16% (4/25), in the F3 cases with platelet count <175,000 μ L⁻¹. There was no case of large varices in the cases with \leq F3 fibrosis and platelet count <175,000 μ L⁻¹.

Applying this platelet count requirement to cirrhotic cases would not enhance the prevalence of large varices in cirrhotic cases but would increase prevalence of large varices in F3 fibrosis. In addition, AASLD and EASL guidelines state that cirrhosis, independent of platelet count, is a risk factor for large esophageal varices. For these reasons, our study only requires a platelet count <175,000 μ L⁻¹ for non-cirrhotic F3 cases. There is no platelet count requirement for enrollment of cases with cirrhosis.

- Meets one of the protocol-defined etiologies for CLD.
- Is scheduled or in the process of being scheduled for EGD.

Selecting Subjects Scheduled for EGD. The target population for application of the HepQuant SHUNT Test is the clinical population with CLD encompassed by our inclusion and exclusion criteria who are selected for EGD for variceal screening.

Categories of Etiology of CLD. We will compare the baseline characteristics of the study population across 5 general etiologic categories: viral, NAFLD/NASH, EtOH, cholestatic disease (PBC, PSC), and other miscellaneous etiologies.

Severity of CLD. The baseline characteristics of three broad categories will be compared: non-cirrhotic F3 fibrosis with platelet count <175,000 μ L⁻¹, compensated cirrhosis (Child-Pugh class A), and mildly to moderately decompensated cirrhosis (Child-Pugh class B).

HepQuant SHUNT Test. The study design is relatively straightforward and simple – one HepQuant SHUNT test is linked to the findings of one EGD performed within 6 weeks of the SHUNT Test. The primary independent variable is DSI from the HepQuant SHUNT Test. The primary dependent variable or endpoint is large esophageal varices on EGD.

The analysis of the CLD Validation Dataset will be similar to the analysis described above for the HALT-C Training Dataset. The minimal model for the HepQuant SHUNT Test will be used and the laboratory analyses have been described elsewhere in this application (see Section 6).

Large and Small Esophageal Varices (EGD finding). The primary endpoint is endoscopically-defined large esophageal varices. The presence of varices is defined as visible venous channels protruding into the esophageal lumen during air insufflation of the esophagus. Large varices are defined as medium, large, Grade 2 or 3, or variceal diameter of 5 mm or more. Varices not meeting criteria for large varices will be classified as small varices.

Any Varices (EGD finding). The endoscopic findings of patients will be defined as either large varices, small varices, or no varices. For the analysis of patients with any varices, patients with large varices will be combined with patients with small varices.

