New varices are unlikely to develop, and small varices are unlikely to become large within 6 weeks. The rate of developing new varices in a cirrhotic patient without varices is approximately 3 to 5%/year (63,64). The rate of small varices enlarging to become large varices is approximately 12-15%/year (64-69). Over 6 weeks these rates would be 0.6% and 1.8%, respectively. Given these slow rates of variceal progression, we conclude that the EGD findings are not expected to change significantly within the 6-week window. Note that the average time interval between the SHUNT test and EGD is likely to be far less than 6 weeks.

The following EGD findings will be recorded:

- Esophageal varices
 - Present or absent; to be categorized as present the varices must protrude into the esophageal lumen during insufflation of the esophagus
 - If varices are present, record size as small (<5 mm diameter, or Grade 1) versus large (5 mm or more in diameter, or Grades 2 or 3)
 - If varices are present, record presence or absence of red wale marks, and whether they are mild, moderate, or severe
- Gastric varices
 - Present or absent
 - If gastric varices are present, record size as small (<5 mm diameter, or Grade 1) versus large (5 mm or more in diameter, or Grades 2 or 3)
 - If gastric varices are present, record presence or absence of red wale marks, and whether they are mild, moderate, or severe
- Portal hypertensive gastropathy
 - o Present or absent
 - o If present, record whether it is mild, moderate or severe

The primary endoscopic endpoint is large esophageal varices. We will also record and report the endoscopic findings of red wale marks, gastric varices, and portal hypertensive gastropathy, but are not planning any formal analysis of these features as endpoints. Red wale marks may amplify risk for variceal hemorrhage in those with esophageal varices – for this reason we will examine the relationship of DSI to red wale marks.

To ensure consistency across centers, all EGDs will be performed by endoscopists experienced in the evaluation and treatment of esophageal varices. The endoscopists will be identified and designated by the clinical center's PI.

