Large Variceal Size. In both the HALT-C Training dataset and the CLD Validation dataset, the primary endpoint is endoscopically-defined large varices. Variceal size described as medium, large, Grade 2 or higher, or variceal diameter of 5 mm or more are classified as LARGE. Varices not meeting criteria for large are classified as SMALL.

Any Varices. The endoscopic findings of patients will be defined as either large varices, small varices, or no varices. For the analysis of patients with any varices, patients with large varices will be combined with patients with small varices.

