6.6 Measures to Minimize Bias: Randomization and Blinding

Randomization:	Not a randomized trial	
Assignment to study groups:	Single Arm study	
Blinding:	 Triple-blind of HepQuant SHUNT Test results Patient Investigator and clinical center HepQuant 	

Single-blind of EGD results – HepQuant

Minimizing Bias: In the study the HepQuant SHUNT Test will be done prior to EGD, a sequence that is true for the clinic. The use of the HepQuant SHUNT test in this study mimics its intended use – i.e., a CLD patient meets sufficient clinical criteria to warrant EGD for screening or surveillance of varices. In the study, the enrolled subjects are scheduled for EGD, and meet these standard clinical criteria. In both the study, and for its intended use in the clinic, the HepQuant SHUNT test is administered after the clinical decision to perform EGD is made but prior to the performance of the EGD. The study results will be used to inform the clinician performing the EGD about the likelihood of large varices to aid in the decision to proceed or avoid the EGD.

Additionally, bias will be further minimized by blinding of patient, investigator and clinical center to the HepQuant SHUNT and DSI results; and, blinding of HepQuant to the EGD results.

Missing Data: Patients who have a DSI score but the EGD results are missing will be classified as "missing data". These patients are censored from the primary analysis which will only include the patients with both EGD results and DSI scores.

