- Administration of the d4-cholate solution orally after addition of flavoring
- Blood sampling at the specified time points
- Serum separation and transfer to transport tubes
- Placement of serum transport tubes into mailer and document shipping
- Recording of any AEs or SAEs related to test administration or procedures
- Completion of the Self-Reported Subject Tolerability Survey

Study Visit 3 (Post-Test Follow-up, 2-30 days after SHUNT test). This post-Test follow-up visit must be done within 30 days after the HepQuant SHUNT Test administration to evaluate the subject for any AEs or SAEs that occurred following Test administration. At least two days must pass between SHUNT test administration and the follow-up visit to allow time for any non-immediate AEs that may occur. The site's PI will perform history and physical exam with a focus on any expected and unexpected AEs and SAEs. Vital signs will be. Blood will be obtained for complete blood count, and serum chemistry. All AEs and SAEs will be recorded.

Collection of EGD Data. The only stipulations regarding the performance of EGD are that it be done after the HepQuant SHUNT Test and that it be done within 42 days after the HepQuant SHUNT test. If convenient for the patient, the EGD can be done on the same day as the HepQuant SHUNT test; but, if this occurs, the EGD must be done after the HepQuant SHUNT test. The coordinator will record concomitant medications, obtain de-identified EGD report and photos, upload the report and photos to the EDC system. and record the EGD results. The findings of the EGD procedure are NOT recorded as Adverse Events.

Defining Large Varices from Endoscopy Reports. The diagnosis of varices and determination of variceal size, as either small or large, will be determined from the source documents reporting the results of the EGD. This same technique was used for varices diagnosis and variceal size determination in the HALT-C Training Dataset. Originally in HALT-C, the varices were recorded as small, medium, or large. But, the category of medium introduced more

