10.2.4 QUALITY ASSURANCE AND QUALITY CONTROL

Each clinical site will perform internal quality management of study conduct, data and biological specimen collection, documentation and completion.

Quality control (QC) procedures will be implemented beginning with the data entry system and data QC checks that will be run on the database will be generated. Any missing data or data anomalies will be communicated to the site(s) for clarification/resolution.

Following written Standard Operating Procedures (SOPs), the monitors will verify that the clinical trial is conducted and data are generated and biological specimens are collected, documented (recorded), and reported in compliance with the protocol and applicable regulatory requirements.

The investigational sites will provide direct access to all trial related sites, source data/documents, and reports for the purpose of monitoring and auditing by the sponsor, and inspection by local and regulatory authorities.

Each participating site will maintain appropriate medical and research records for this trial, in compliance with regulatory and institutional requirements for the protection of confidentiality of participants.

As part an FDA regulated study, each site will permit authorized representatives of the IDE Sponsor, and regulatory agencies to examine (and when permitted by applicable law, to copy) clinical records for the purposes of quality assurance reviews, audits, and evaluation of the study safety, progress, and data validity.

The persons with access to these records will be listed in the site delegation log.

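### The default-to-small rule for variceal size records a varix of unreported size as a non-case in the primary 2x2 table, instead of as an unknown reference result

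*Combined protocol and SAP*

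**What the plan says.** The primary reference result is large esophageal varices on EGD. Five places in the combined protocol and SAP bear on how it is coded.

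- **Section 4.3.1 (validation dataset).** "Large varices are defined as medium, large, Grade 2 or 3, or variceal diameter of 5 mm or more". The default follows: "Varices not meeting criteria for large varices will be classified as small varices".
- **Section 4.2.1.** "Variceal size described as medium, large, Grade 2 or higher, or variceal diameter of 5 mm or more are classified as LARGE", again with everything else going to small. The paragraph covers both datasets: "In both the HALT-C Training dataset and the CLD Validation dataset, the primary endpoint is endoscopically-defined large varices".
- **Section 4.1.2 (EGD findings to record).** "If varices are present, record size as small (<5 mm diameter, or Grade 1) versus large", where large is 5 mm or more, or Grades 2 or 3. Small is defined positively here.
- **Section 8.1.** Presence and size "will be determined from the source documents reporting the results of the EGD".
- **Section 6.6.** "Patients who have a DSI score but the EGD results are missing will be classified as" missing data, and these patients leave the primary analysis. Nothing is said about an EGD that was done and showed varices but gave no size.

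Section 10.2.4 adds a general query process: "Any missing data or data anomalies will be communicated to the site(s) for clarification/resolution".

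**The concern.** The EGD is a routine-care procedure at up to 40 sites, and size is read from its report. No section requires that report to state a size, grade or diameter. If it says only that varices are present, section 4.1.2 supports neither small nor large, while sections 4.2.1 and 4.3.1 make the varix small. An unknown reference result then enters the primary table as a negative one. The size field is also complete at that point, so the query process in section 10.2.4, which responds to missing or anomalous data, has nothing to react to.

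Both success criteria, the upper confidence limit for NLR and the observed sensitivity, come from that table. The expected number of large varices is only 80, with 8 misses at the design sensitivity, so a few recoded cases can matter.

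**Working it through.** **Inputs.** Section 9.2.1: 400 evaluable subjects, 80 with large varices and 320 without; sensitivity 0.90, specificity 0.50, NLR 0.20; null NLR 0.52. Table 9, equation E: variance of ln NLR. Section 9.5.1: final success needs the upper limit of the 96.07% score interval below 0.52 and observed sensitivity at least 0.85. The documents give no rate of unsized reports, so every rate below is an assumption.

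**Plan's own figure.** Variance = 0.9/(0.1 × 80) + 0.5/(0.5 × 320) = 0.1156, so SE = 0.340. Power = Φ(ln(0.52/0.20)/0.340 − 1.96) = 0.802, against 0.80 in Table 10.

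**How recoding moves cells.** The design table is TP 72, FN 8, FP 160, TN 160. Let u be the share of the 80 large varices that are unsized, and s the sensitivity among them. Then TP = 72 − 80us, FN = 8 − 80u(1−s), FP = 160 + 80us, TN = 160 + 80u(1−s). Here FNR is 1 − NPV, as the protocol defines it.

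| Scenario | Sensitivity | Specificity | NLR | FNR |
|---|---|---|---|---|
| Correct coding | 0.900 | 0.500 | 0.200 | 4.8% |
| u = 10%, s = 0.90 (random) | 0.900 | 0.490 | 0.204 | 4.3% |
| u = 10%, s = 0.70 | 0.922 | 0.495 | 0.157 | 3.3% |
| u = 10%, s = 0.70, excluded instead | 0.922 | 0.500 | 0.156 | 3.4% |

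**Power under random non-reporting (u = 10%).** Cases fall to 72. Variance = 0.9/(0.1 × 72) + 0.510/(0.490 × 328) = 0.128, SE = 0.358, power = Φ(ln(0.52/0.204)/0.358 − 1.96) = 0.74. At u = 5% it is 0.77, and at 15% it is 0.71.

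**Direction.** Suppose 10 large varices are recoded and a fraction f of them have DSI at or below 18.3. NLR is unchanged when (8 − 10f)/70 = 0.20 × (160 + 10f)/330, that is at f = 0.116. Above about 12% the default favours the test, and below that it counts against it.

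**Borderline results** (specificity 0.50 before recoding):

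| Table | Sensitivity | 96.07% upper limit | Result |
|---|---|---|---|
| 13 of 80 missed | 0.8375 | 0.536 | fails |
| one of those misses coded small (12 of 79) | 0.848 | 0.511 | fails on sensitivity |
| two of those misses coded small (11 of 78) | 0.859 | 0.485 | passes |
| 12 of 80 missed | 0.850 | 0.507 | passes |
| one detected case coded small (12 of 79) | 0.848 | 0.514 | fails on sensitivity |

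**Pass probability at true NLR 0.52, sensitivity 0.90** (simulation with 80 cases, 95% score interval, no interim analysis, 5 to 10% of large varices unsized). Correct coding gives 0.017, which matches Table 12. Random non-reporting gives 0.015 to 0.016. If missed cases are twice as likely to be unsized it is 0.022 to 0.028, and if four times as likely, 0.034 to 0.067. In the four-fold, 10% case, excluding unsized varices instead of coding them small gives 0.061 against 0.067.

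**The case against.** The strongest reply is that size is a required entry. Section 4.1.2 asks for it whenever varices are present and does not let an unsized varix qualify as small. Endoscopists are experienced and designated by the site investigator, reports and photos are uploaded, section 10.2.3 directs monitoring at endoscopy data, and section 10.2.4 provides queries. The eCRF is not among the documents and may already allow for an unstated size. Section 6.6 could also be read as treating an undetermined size as a missing EGD result. These controls make the problem less frequent. They do not override the default in sections 4.2.1 and 4.3.1, and none of them says what to do with a report that gives no size.

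Three stronger readings are tempting, and the documents do not support them.

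- **The rule flatters the test.** Only unsized large varices with DSI at or below 18.3 become true negatives. Sites are blinded to DSI, and random non-reporting leaves sensitivity at 0.90 and moves NLR slightly the wrong way for the test. A favourable bias needs unsized large varices to have lower DSI than other large varices. The training data make a link through size plausible: 30 of 52 small varices (58%) had DSI above 18.3, against 21 of 22 large ones (95%). That unsized varices lie near 5 mm is still an assumption, as is the 0.70 sensitivity used above.
- **Grade 4 varices are coded small.** That follows only if section 4.3.1 or 4.1.2 is read alone. Section 4.2.1, which covers both datasets, and section 2.2.2 use an open-ended grade. This is a wording mismatch to reconcile, not an established miscoding.
- **The trial's power is 0.74.** Equation E is the approximation used to choose the sample size. The plan's simulated power at this design point is 0.916 without the interim analysis and 0.855 with it (Table 12).

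**Conclusion.** The point holds as a defect in a stated rule. Followed literally, sections 4.2.1 and 4.3.1 turn an unknown variceal size into a negative reference result, in conflict with the positive definition of small in section 4.1.2 and outside the missing-data rule in section 6.6. Unsized varices that are truly small are coded correctly; the harm is confined to unsized large ones.

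The size of the effect cannot be fixed from the documents, because they give no rate of unsized reports. Under an assumed 10% at random, the loss is in precision (equation E power 0.80 to 0.74), and FNR reads 4.3% instead of 4.8%. If missed cases are more likely to be unsized, sensitivity and NLR look better than they are. Either way, one or two recoded cases can reverse a borderline result. The remedy is cheap enough to adopt without knowing the frequency.

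**What to change.** In sections 4.1.2, 4.2.1, 4.3.1 and 8.1, use one positive definition of each class: small if stated as small, Grade 1 or under 5 mm; large if stated as medium or large, Grade 2 or higher, or 5 mm or more. Code anything else as size not determined. Send these to the performing endoscopist as a data query, blind to DSI, to be answered from the report and photos already uploaded.

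State how unresolved cases enter the primary analysis, and pre-specify two sensitivity analyses of the primary endpoint: all unresolved cases counted as large, and all counted as small. Excluding them is not enough alone, because it leaves almost the same bias when non-reporting is related to size (NLR 0.156 excluded, 0.157 coded small, against a true 0.200).

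The cost is one extra CRF category, some queries, and possibly a few subjects whose size stays unresolved.
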